#### **8.7.14 Treatment record**

At every visit after the randomization visit (6 weeks, 3 months, 6 months, 9 months and 18 months), the outcome assessor should record several parameters of the ongoing physiotherapy program:

- Frequency of training
- Duration of training
- Home exercises
- Use of electrostimulation
- Total number of physiotherapy sessions
- Other therapies (vitamin substitution, acupuncture, ...)

Other therapies are allowed, as long as they reflect daily practice. These therapies should be thoroughly noted in the eCRF. This registration is not considered standard of care.

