### 8.4 Blinding

Blinding of trial participants and care providers is not possible because of obvious differences between both treatment groups: one group will be surgically treated whereas the other group will receive maximal conservative treatment until the primary endpoint is assessed. However, the clinical investigator in the foot drop trial (= outcome assessor) can be blinded to treatment. All participants will be asked to wear long trousers to cover a potential scar at the level of the knee. Furthermore, all patients will be asked to apply a bandage at the site of the operation (or the site of entrapment if there was no operation). Participants are not allowed to discuss their treatment with the outcome assessor. A preassessment contact between the patient and an unblinded member should be organized prior to the study assessments, to remind and instruct patients of the blinding precautionary measures.

Patients in the surgical arm of the trial will be evaluated after 10 days. A postoperative control is considered standard of care. Assessments cannot be performed by the outcome assessor at this stage, as this will cause unblinding.

Since all health care providers have access to the electronic health record, measures should be taken to prevent unblinding of the outcome assessors. Several precautions should be considered:

- Data of assessments will be documented on a separate worksheet, outside the electronic health record so that there will be no need to access the electronic health record.
- If the outcome assessor thinks the electronic health record should be accessed, the treating physician should be consulted. Since the treating physician is not blinded, he/she can access the electronic health record if deemed necessary.

To avoid errors, the outcome assessor must be aware of the identity of the patient during the assessments. Therefore, anonymization during assessment is not possible.

Blinding the outcome assessor will create the opportunity to make an objective assessment of primary and (key) secondary outcome parameters, without increasing the risk of bias.

Until the time of unblinding for final data analysis, the randomization list is kept strictly confidential. The randomization list is accessible only by the REDCap data manager to prevent further selection bias. The statistician should neither have access to randomized treatments (or randomization list) nor even to the full database until the database has been locked for analysis.

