## 8.7 Trial assessments

In the section below, all study procedures and trial assessments are described, as well as their timing. Several assessments will be performed by the treating physicians, others by the outcome assessor (blinded researcher). The study assessments are listed in the visit and assessment schedule (see Section 8.8).

A list of standard assessments (clinical records, considered daily practice; including motor and sensory function, ability to walk (barefoot), need for orthosis, treatment) will be composed for uniformity across centers. These data will be collected at every study visit and will be recorded in the eCRF. The list of standard assessments is included in appendix 4.

Several questionnaires (EQ-5D 5L, WPAI) will be made available as an online survey (REDCap) for patients. All other questionnaires completed by the subject or proxy are entered into the corresponding eCRF form by the study coordinator. The original paper copies of the questionnaires that are not available online will be filed in the ISF and made available for verification by the site monitor. If patients fail to complete the survey online, the blinded researchers can make sure that the questionnaires are complete during follow-up. If the patient is unable to return to the investigative site for study specific follow-up, the questionnaires will be sent to the patient's home (and the clinical evaluation will be recorded as missing data). Patients will receive a message prior to each evaluation moment, to remind them of the upcoming assessments. At every assessment, the schedule of the assessments to come will be discussed with the patients as an extra reminder.

If visits or data collection time-points are missed, despite previous mentioned efforts, following measures will be taken:

- The outcome assessor will inform the treating physician, PI, clinical trial assistant or any other non-blinded study personnel. The patient will be contacted to reschedule the visit as soon as possible. This cannot be done by the outcome assessor to guarantee blinding.
- If the patient is not able to reschedule, the reason will be documented in the eCRF. If possible, certain assessments will be evaluated through telephone:
  - o EQ-5D 5L questionnaire

- WPAI questionnaire
- Sensory changes
- Ability to walk barefoot
- Need for foot-ankle orthosis
- Return to work
- Registration of treatment

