The 6MWD will be evaluated twice at each visit (as first and last assessment), taking the 'learning effect' into account. Furthermore, the applied reference values are based on repeated 6MWD. Best 6MWD will be documented in the eCRF.

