### **8.8 Table of trial procedures**

TABLE OF TRIAL PROCEDURES	SCREENING	RANDOMIZATION !	TREATMENT PERIOD					EXTENDED FU PERIOD CROSS- OVER PATIENTS
			DAY 0	FU 10D (+4D) surgery	FU 6W (+ 1W)	FU 3M (+ 2W)	FU 6M (+ 2W)	FU 18M (+ 3w)
INFORMED CONSENT	TP							
MEDICAL HISTORY	TP							
ELIGIBILITY CRITERIA	TP							
CONTRIBUTING FACTORS	TP							
EDX	TP*					*		*
ISOMETRIC DYNAMOMETRY		BR	TP	BR	BR	BR	BR	BR
6MWT		BR		BR	BR	BR	BR	BR
10MWT		BR		BR	BR	BR	BR	BR
RETURN TO WORK				BR/P				
FUNCTIONAL AMBULATION CATEGORIES		BR		BR	BR	BR	BR	BR
NEED FOR ORTHOSIS		BR		BR	BR	BR	BR	BR
ABILITY TO WALK BAREFOOT		BR		BR	BR	BR	BR	BR
STANMORE QUESTIONNAIRE		BR		BR	BR	BR	BR	BR
EQ5D-5L QUESTIONNAIRE		BR/P	TP/P	BR/P	BR/P	BR/P	BR/P	BR/P
SURGICAL COMPLICATIONS			TP	TP				TP
SENSORY CHANGES	TP	TP/BR	TP	BR	BR	BR	BR	BR
TREATMENT RECORD		BR		BR	BR	BR	BR	BR
WPAI		BR/P		BR/P		BR/P		
ADVERSE EVENTS					TP			
SERIOUS ADVERSE EVENTS					TP			
LEGEND	TP = treating physician; BR = blinded researcher (outcome assessor); bold = standard of care; P = patient (online survey); red = primary endpoint; FU = follow-up; D = days; W = weeks; M= months, YR = year *investigation performed by neurologist / rehabilitation physician, data collection in eCRF by study coordinator Some assessments are done by both the treating physician and blinded researcher to prevent bias/unblinding ! = surgery maximum one week after randomization, preferably within 2 days							

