## 9.2 Conservative treatment

Evidence on the conservative management of foot drop is scarce. Willerslev-Olsen et al. (115) found a significant improvement of foot and great toe dorsiflexion in children with cerebral palsy and foot drop after 1 month of gait training. Despite the lack of studies on training to improve foot drop of peripheral origin (as in peroneal neuropathy), a training program is recommended for every patient with foot drop (116). Goals of the treatment are to reduce muscle fiber atrophy, to preserve ankle mobility and to improve gait in general.

A basic standard protocol for physiotherapy is proposed. However, the protocol should be adapted to the clinical presentation and needs of every individual patient. So, if the trial should be mirroring daily practice, some degree of freedom in the conservative treatment should be allowed.

Standard instructions for the physiotherapist will be provided:

- Mobilization of ankle and foot, stretching of the calf muscles (prevention of contractures)
- Tonification of the dorsiflexion- and eversion muscles of the ankle
- Proprioceptive training
- Gait rehabilitation
- Home exercise schedule

Intensity: 60 sessions (F-pathology, Belgium) at a frequency of 1/2 sessions per week, with a possibility of a higher frequency during the first months.

The training program should be progressive. To evaluate the compliance, the patients will be asked to complete a training diary.

We do not advice to use electrostimulation because of the lack of training of younger physiotherapists and the lack of good equipment. The use of electrostimulation is not prohibited. We do not routinely support the use of an orthosis during the first six weeks. Most patients receive a prefabricated orthosis at this stage. However, this does not always meet the requirements of the patients at later stages. When the foot drop is irreversible, an ankle foot orthosis can help to improve everyday mobility.

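### The blinded outcome assessor must ask patients about their physiotherapy at five follow-up visits, although Section 8.4 forbids patients to discuss treatment with the assessor

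*Protocol*

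**What the plan says.** Patients and care providers know the allocation, so the protocol relies on a blinded outcome assessor. Section 8.4 has patients cover the knee with long trousers and a bandage, keeps the assessor out of the health record, and adds: "Participants are not allowed to discuss their treatment with the outcome assessor". Section 8.7 goes further. When a visit is missed, unblinded staff must contact the patient to reschedule, because "This cannot be done by the outcome assessor to guarantee blinding".

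Section 8.7.14 then states that, at 6 weeks and at 3, 6, 9 and 18 months, "the outcome assessor should record several parameters of the ongoing physiotherapy program". The items are frequency, duration, home exercises, electrostimulation, total sessions and other therapies. The table in Section 8.8 gives the treatment record the code BR at follow-up, and its legend reads "BR = blinded researcher (outcome assessor". Appendix 4 puts the treatment items on the same list as the MRC score.

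On the primary outcome test, Section 8.7.5 says "The 6MWD will be evaluated twice at each visit (as first and last assessment", and then "Best 6MWD will be documented in the eCRF". The outcome assessor performs each test.

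**The concern.** A site cannot ask the treatment questions and also keep the patient from discussing treatment with the person asking. The questions are informative because physiotherapy is the treatment that defines the control arm. Section 9.2 proposes "Intensity: 60 sessions (F-pathology, Belgium) at a frequency of 1/2 sessions per week" for conservative care. Section 5.1 only permits physiotherapy after surgery and leaves its amount to the treating physician. The field for other therapies is free text, so an operation could also be mentioned there.

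At stake is detection bias. The assessor encourages the patient every minute of the six-minute walk and scores MRC for ankle dorsiflexion. The first produces the primary endpoint. An MRC score of at least 4 is one of the two conditions for recovery in the key secondary endpoint.

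**Working it through.** The point rests on setting sections side by side, not on a figure in the plan. The only plan figure used is the enrolment total, and it reproduces: 86 per arm (172) gives 90.3% power for an effect size of 0.5 with a two-sided 5% t-test, and 172 / 0.95 = 181.05, rounded up to 182.

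**Who does what**

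- Treatment record at five follow-up visits: outcome assessor (8.7.14; 8.8).
- Talk about treatment with the outcome assessor: forbidden (8.4).
- Rescheduling call after a missed visit: not by the outcome assessor, to protect blinding (8.7).
- Every six-minute walk: outcome assessor (8.7.5).
- MRC score from 6 weeks onward: outcome assessor (8.7.3).
- Contact before the assessments: an unblinded team member (8.4, 8.5).

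**Order of events**

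1. The two walks are the first and last assessments of a visit. A treatment record taken among that visit's assessments therefore falls before the closing walk. The protocol does not state the form's position, but Section 8.7 includes treatment in the standard assessments collected at each study visit.
2. The better distance is kept, so the closing walk can set the recorded value.
3. At 6 weeks the opening walk precedes any record. At 9 months, three earlier records (6 weeks, 3 and 6 months) precede both walks, and the 9-month record can precede the closing one.
4. In Appendix 4 the MRC score stands ahead of the treatment items, so MRC at the same visit may be scored first. MRC at later visits follows the earlier records.

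**Extent of exposure** (forms, not biased measurements)

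- Records per patient: 4 up to and including 9 months; 4 + 1 = 5 up to 18 months.
- Patients: 182 with no dropout; 182 − 9 = 173 if the expected 5% (n = 9) contribute none.
- By the primary endpoint: 173 × 4 = 692 to 182 × 4 = 728.
- In total: 173 × 5 = 865 to 182 × 5 = 910.

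Only the first range bears on the primary endpoint. The 10-day surgical visit is not affected: the treating physician conducts it and the table has no treatment record there.

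**A separate mismatch.** Section 8.7.13 gives surgical complications after cross-over, at 18 months, to the outcome assessor. The table gives them to the treating physician (TP). Such a form reveals surgery directly, but it can touch only 18-month secondary outcomes.

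**The case against.** The strongest reply is that the ban in 8.4 follows the trousers and bandage rules and may be meant to hide surgery only, whereas 8.7.14 asks both arms a set list with no surgery item. That reading is possible but not written: the sentence covers treatment without limit, and physiotherapy is the control arm's treatment.

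A second reply is that the cue is weak. Section 14.2 reports that many operated patients also had physiotherapy, Section 11.5 expects physiotherapy costs in both arms, and conservative care is individualised. This stands. The protocol gives no session counts by arm after randomisation, so how well the answers separate the arms is unknown.

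Third, several safeguards limit the effect: at least two trained assessors per site, the preassessment contact, training videos with a questionnaire, a standardised walk with example wording and counted laps, and steering committee experts who follow up blinding. Carry-over also requires the same assessor to remember answers for weeks or months. These points reduce the likely effect but do not make 8.4 and 8.7.14 compatible.

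Finally, the counts above measure forms and not bias. That is correct, and no more is claimed for them.

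**Conclusion.** The contradiction holds, and it concerns the trial's main protection against assessor bias. What is shown is an avoidable cue to allocation, not certain unblinding. It can reach the 9-month walk distance and the MRC part of the recovery endpoint. Its effect on the treatment estimate cannot be computed from the protocol.

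The conclusion rests on two assumptions: that the treatment record is taken among the visit's assessments, and, for carry-over between visits, that the same assessor continues with the patient. The conflict between 8.4 and 8.7.14 needs neither. It should be corrected, although it does not invalidate the design.

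**What to change.** In 8.7.14, Appendix 4 and the treatment record row of the 8.8 table, assign the record to the unblinded team member who holds the preassessment contact, and remove the treatment items from the assessor's worksheet. Separately, reconcile 8.7.13 with the table so that the blinded assessor does not complete a surgical complications form at 18 months.

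The cost is an edit to text and forms, plus six items added to a contact that is already planned. No visit or data item is added, and the session counts needed for the economic evaluation are kept. The items need no examination: Section 8.7 lists "Registration of treatment" among the things that can be done by telephone, although it does not say who makes that call. The training diary is not a ready substitute, because it is described only under conservative treatment.

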#### **8.7.15 Work Productivity and Activity Impairment Questionnaire: General Health (WPAI:GH)**

Health economic aspects of foot drop will be evaluated through the Work Productivity and Activity Impairment Questionnaire (WPAI). The WPAI is widely used and validated in multiple languages. The WPAI allows for assessment of employment and professional productivity among other features. Participants will fill in the WPAI at baseline, 6 weeks and 6 months. WPAI will be available online. If the patient receives allowances, the amount will be noted for economic analysis. This is not considered standard of care. The English version of the WPAI is included in Appendix 7.

#### **8.7.16 Return to work at six weeks after randomization**

Health economic aspects will also be evaluated through the assessment of return to work. We expect subgroups of patients with foot drop to be unable to work. Once the foot drop has improved (or fully recovered), we expect patients to be able to return to work and to not experience any more related problems (after their initial recovery). In this trial population foot drop does in general not represent a chronic condition with periods of relapse. Either the foot drop recovers enough to be able to work again, or the foot drop does not sufficiently recover to resume previous professional activities.

Taking this into account, return to work seems to represent a very important measure. Patients will be asked about return to work at the study visit six weeks after randomization. To avoid recall bias, patients will be asked in advance to record the date of return to work. During baseline assessments, subjects will be questioned if they are incapacitated to work due to the foot drop and the last working day will be recorded in the eCRF.

We anticipate the biggest difference in return to work between the two groups at six weeks after randomization. We expect patients to recover faster after neurolysis. Therefore, we expect that a significant majority in the surgically treated group will be able to return to work six weeks after randomization (equals five to six weeks after surgery), whereas recovery could be slower in the conservative group. Recovery from surgery itself is generally fast, thus we do not expect that surgical recovery has a big impact on return to work but of course this issue will also be tackled in the trial.

### **8.8 Table of trial procedures**

TABLE OF TRIAL PROCEDURES	SCREENING	RANDOMIZATION !	TREATMENT PERIOD					EXTENDED FU PERIOD CROSS- OVER PATIENTS
			DAY 0	FU 10D (+4D) surgery	FU 6W (+ 1W)	FU 3M (+ 2W)	FU 6M (+ 2W)	FU 18M (+ 3w)
INFORMED CONSENT	TP							
MEDICAL HISTORY	TP							
ELIGIBILITY CRITERIA	TP							
CONTRIBUTING FACTORS	TP							
EDX	TP*					*		*
ISOMETRIC DYNAMOMETRY		BR	TP	BR	BR	BR	BR	BR
6MWT		BR		BR	BR	BR	BR	BR
10MWT		BR		BR	BR	BR	BR	BR
RETURN TO WORK				BR/P				
FUNCTIONAL AMBULATION CATEGORIES		BR		BR	BR	BR	BR	BR
NEED FOR ORTHOSIS		BR		BR	BR	BR	BR	BR
ABILITY TO WALK BAREFOOT		BR		BR	BR	BR	BR	BR
STANMORE QUESTIONNAIRE		BR		BR	BR	BR	BR	BR
EQ5D-5L QUESTIONNAIRE		BR/P	TP/P	BR/P	BR/P	BR/P	BR/P	BR/P
SURGICAL COMPLICATIONS			TP	TP				TP
SENSORY CHANGES	TP	TP/BR	TP	BR	BR	BR	BR	BR
TREATMENT RECORD		BR		BR	BR	BR	BR	BR
WPAI		BR/P		BR/P		BR/P		
ADVERSE EVENTS					TP			
SERIOUS ADVERSE EVENTS					TP			
LEGEND	TP = treating physician; BR = blinded researcher (outcome assessor); bold = standard of care; P = patient (online survey); red = primary endpoint; FU = follow-up; D = days; W = weeks; M= months, YR = year *investigation performed by neurologist / rehabilitation physician, data collection in eCRF by study coordinator Some assessments are done by both the treating physician and blinded researcher to prevent bias/unblinding ! = surgery maximum one week after randomization, preferably within 2 days							

## 8.9 Withdrawal criteria

Participants may voluntarily discontinue from Trial treatment and/or prematurely end their participation in the Trial for any reason at any time. In such case, the Investigator must make a reasonable effort to contact the participant (e.g. via telephone, e-mail, letter) in order to document the primary reason for this decision.

The Investigator may also decide at any time during the course of the Trial, to temporarily interrupt or permanently discontinue the Trial treatment if it is deemed that continuation would be detrimental to, or not in the best interest of the participant.

Similarly, the Sponsor, Ethics Committee or authorized regulatory authority can decide to halt or prematurely terminate the Trial when new information becomes available whereby the rights, safety and well-being of Trial participants can no longer be assured, when the integrity of the Trial has been compromised, or when the scientific value of the Trial becomes obsolete and/or unjustifiable.

The study design does not allow any cross-over to the other treatment arm until the primary endpoint is reached (9 months after randomization). Conservative care patients have the opportunity to undergo surgery after 9 months.

Subjects are considered withdrawn from the study if they:

- Are not willing to be followed up for the purposes of the trial at any further visits.
- State an intention to withdraw further participation in all components of the study.
- Are lost for follow-up (if all repeated attempts by the study-team to communicate with the individual have failed. The site and study team must take preventive measures to avoid a subject being lost to follow-up (at least 3 contacts (e.g., telephone calls, or e-mails) must be placed to the last available telephone number or e-mail address) and 1 registered letter must be sent by post to the last available home address. If the subject is still unreachable after all contact attempts listed above, he/she will be considered to be lost to follow-up.) In the source documents will be documented which steps have been taken to contact the participant.

Subjects are considered withdrawn from treatment if:

- The patient and/or patient's guardian does not wish to continue with further trial intervention.
- Choose for treatment in other arm (cross-over from conservative treatment to surgery).

A patient withdrawn from further treatment should remain in follow-up

Subjects are considered withdrawn from consent if:

- He/she withdraws consent to take part in the study without having to give a reason, and that may mean withdrawing his/her consent to the processing of health data.

If a subject withdraws consent, no further data will be collected in the eCRF from the date of withdrawal onward.

The details of withdrawal should be clearly documented in the patient's medical records and in the eCRF.

In the sample size of 182 subjects, there is an expected 5% dropout of patients (n=9). These subjects will not be replaced.

The sponsor reserves the right to terminate the study at any time globally or locally.

If a study is prematurely suspended or terminated, the sponsor will promptly inform the investigators and the Ethics Committee and provide the reasons for the suspension or termination. If the study is suspended or prematurely terminated for any reason, the investigator — in agreement with the sponsor — must promptly inform all enrolled subjects who are still in the study and/or their proxies/legal representatives (as applicable) and ensure appropriate treatment and follow-up.

